8.3 Safety Analysis

Adverse events will be coded to system organ class and preferred terms using the Medical Dictionary for Regulatory Activities (MedDRA, Version 20 or higher).

Frequency and percentage of subjects reporting TEAEs will be tabulated overall and for each treatment in PRO 2018-02 by preferred terms and further by severity and relationship to study device. In summaries of severity and relationship, subjects reporting more than one event in a treatment arm that are mapped to the same preferred term will be counted only once in that treatment arm under the strongest severity and relationship, respectively. In addition, visual related TEAEs will be summarized separately by preferred term.

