5.6 Safety Variables

Key safety variables include incidence rate of treatment-emergent adverse events (TEAEs) and the exposure to the study product, as well as Investigator Ease of Use Assessment, lip function, lip sensation, lip texture, lip firmness, lip symmetry, and lip movement/function.

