5.6.1 Adverse Events

All adverse events (AEs) occurring during the study will be recorded and coded in the Medical Dictionary for Regulatory Activities (MedDRA), version 20 or higher. TEAEs are defined as events that appear subsequent to the open-label injection or that were present prior to the open-label injection but worsened in intensity after the open-label injection.

TEAEs (those related to vascular injections/Visual events, separate from those that were not related to vascular injections/Visual events) for the retreated subjects will be summarized grouped by the number of injections that were received of PN40082, or Restylane Silk during the prior controlled study (PRO 2018-02). Frequency and percent of subjects reporting TEAEs of injection site will be tabulated by preferred terms, and further by severity and relationship to study device. In summaries of severity and relationship, subjects who reported more than one event in a treatment arm that are mapped to the same preferred term will be counted only once in that treatment arm under the strongest severity and relationship, respectively.

TEAEs related to vascular injections/Visual events will also be tabulated by subject Fitzpatrick Skin Type (I-III vs. IV-VI), each Fitzpatrick Skin Type individually and by number of injections subjects received.

Treatment-Emergent Serious Adverse Events (TESAEs) and TEAEs that led to treatment interruption or discontinuation will be presented in data listings.

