5.6.3 Other Variables

Investigator Ease of Use Assessment

Overall ease of use of the device will be evaluated by the Treating Investigator using the numerical rating scale (NRS) from 0 being not easy to 10 being most easy at Visit 1/Day. It will be summarized for all retreated subjects descriptively with mean, SD, minimum, median, and maximum.

Lip Evaluations

Lip function, lip sensation, lip texture, lip firmness, lip symmetry, and lip movement/function will be evaluated by the Blinded Evaluating Investigator at each visit. These variables will be summarized using frequency and percent of subjects by categories of incidence.

Concomitant Medications

Concomitant medications will be coded using the World Health Organization (WHO) Drug Dictionary, Version March 2013 or later, and will be presented in data listings.

6 Tables and Listings

The following is an example of tables and listings that will be included in the clinical study report. Tables and listings may be modified as needed during the data analyses.

7 Appendices

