¹ Denominator is the number of TEAEs related to vascular injections/visual event reported by all subjects who received the corresponding treatment.

² Denominator for percentages by severity is the number of subjects with respective TEAEs after receiving the corresponding treatment. Numerator (count of subjects) is based on the rule that subjects reporting more than one same incidence associated with a treatment arm are counted only once for the treatment arm under the greatest reported severity.

Source: Listing 16.2.7.1.1

O:\Studies\Prollenium\SYM 2018-03\Biometrics\Programs\Tables\xxx.sas ran on Month Day, Year at hh:mm on data from Month Day, Year.

Table 14.3.2.8 – Duration of Most Frequently Occurring Treatment-Emergent Adverse Events (TEAEs) Related to Vascular Injections/Visual Events by MedDRA Preferred Term

Preferred Term	Treatment Group In PRO 2018-02	Events % (n/N) ¹	<7 Days % (n/N) ²	7-30 Days % (n/N) ²	>30 Days % (n/N) ²
Term 1	PN40082	0% (0/0)	0% (0/0)	0% (0/0)	0% (0/0)
	Restvlane Silk	0% (0/0)	0% (0/0)	0% (0/0)	0% (0/0)
	Total	0% (0/0)	0% (0/0)	0% (0/0)	0% (0/0)
Term 2	PN40082	0% (0/0)	0% (0/0)	0% (0/0)	0% (0/0)
	Restvlane Silk	0% (0/0)	0% (0/0)	0% (0/0)	0% (0/0)
	Total	0% (0/0)	0% (0/0)	0% (0/0)	0% (0/0)
...					
...					
...					

Most frequently occurring TEAEs related to vascular injections/visual event are those that were reported by 5% or more of the total retreated subjects.

¹ Denominator is the number of TEAEs related to vascular injections/visual event reported by all subjects who received the corresponding treatment.

² Denominator for percentages by severity is the number of subjects with respective TEAEs after receiving the corresponding treatment. Numerator (count of subjects) is based on the rule that subjects reporting more than one same incidence associated with a treatment arm are counted only once for the treatment arm under the longest duration.

Source: Listing 16.2.7.1.1

O:\Studies\Prollenium\SYM 2018-03\Biometrics\Programs\Tables\xxx.sas ran on Month Day, Year at hh:mm on data from Month Day, Year.

Table 14.3.2.9 – Overall Summary of Treatment-Emergent Adverse Events (TEAEs) Related to Vascular Injections/Visual Events

	PRO 2018-02 PN40082		PRO 2018-02 Restvlane Silk		Total	
	Subjects ¹ (N=xx)	Events ² (N=xx)	Subjects ¹ (N=xx)	Events ² (N=xx)	Subjects ¹ (N=xx)	Events ² (N=xx)
Overall	0 (0%)	0 (0%)	0 (0%)	0 (0%)	0 (0%)	0 (0%)
Duration						
Less than 1 week	0 (0%)	0 (0%)	0 (0%)	0 (0%)	0 (0%)	0 (0%)

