Between 1 week and 1 month (30 days)	0 (0%)	0 (0%)	0 (0%)	0 (0%)	0 (0%)	0 (0%)
More than 1 month (30 days)	0 (0%)	0 (0%)	0 (0%)	0 (0%)	0 (0%)	0 (0%)
Severity						
Mild	0 (0%)	0 (0%)	0 (0%)	0 (0%)	0 (0%)	0 (0%)
Moderate	0 (0%)	0 (0%)	0 (0%)	0 (0%)	0 (0%)	0 (0%)
Severe	0 (0%)	0 (0%)	0 (0%)	0 (0%)	0 (0%)	0 (0%)
Causality						
Treatment-related*	0 (0%)	0 (0%)	0 (0%)	0 (0%)	0 (0%)	0 (0%)
Not treatment-related	0 (0%)	0 (0%)	0 (0%)	0 (0%)	0 (0%)	0 (0%)
Outcome						
Resolved	0 (0%)	0 (0%)	0 (0%)	0 (0%)	0 (0%)	0 (0%)
Improved	0 (0%)	0 (0%)	0 (0%)	0 (0%)	0 (0%)	0 (0%)
Stabilized	0 (0%)	0 (0%)	0 (0%)	0 (0%)	0 (0%)	0 (0%)
Worsened	0 (0%)	0 (0%)	0 (0%)	0 (0%)	0 (0%)	0 (0%)
Unchanged	0 (0%)	0 (0%)	0 (0%)	0 (0%)	0 (0%)	0 (0%)
Treatment Required (Action Taken)						
None	0 (0%)	0 (0%)	0 (0%)	0 (0%)	0 (0%)	0 (0%)
Study treatment interrupted/discontinued	0 (0%)	0 (0%)	0 (0%)	0 (0%)	0 (0%)	0 (0%)
Non-drug therapy	0 (0%)	0 (0%)	0 (0%)	0 (0%)	0 (0%)	0 (0%)
New OTC or Rx drug added	0 (0%)	0 (0%)	0 (0%)	0 (0%)	0 (0%)	0 (0%)
Hospitalized (includes ER visits)	0 (0%)	0 (0%)	0 (0%)	0 (0%)	0 (0%)	0 (0%)

¹ Denominator is the number of subjects who received the corresponding treatment.

² Denominator is the number of adverse events reported by subjects who received the corresponding treatment.

*Treatment-related includes Possibly and Probably Related.

For Severity and Causality, subjects reporting more than one TEAE related to vascular injections/visual event associated with a treatment arm are counted only once for the treatment arm under the greatest reported severity and most likely causality, respectively.

For Duration, Outcome and Treatment Required (Action Taken), at each level of the categories, subjects reporting more than one TEAE related to vascular injections/visual event associated with a treatment arm are counted only once for the treatment arm at that category level.

Source: Listing 16.2.7.1.1

O:\Studies\Prolenium\SYM 2018-03\Biometrics\Programs\Tables\xxx.sas ran on Month Day, Year at hh:mm on data from Month Day, Year.

Note:

Tables 14.3.2.1, 14.3.2.2, 14.3.2.3, 14.3.2.4 will be used as the shell for the following tables:

Table 14.3.3.1 – Treatment-Emergent Adverse Events (TEAEs) Excluding Vascular Injections/Visual Events by MedDRA System Organ Class and Preferred Term

Table 14.3.3.2 – Treatment-Emergent Adverse Events (TEAEs) Excluding Vascular Injections/Visual Events by MedDRA System Organ Class, Preferred Term, and Severity

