O:\Studies\ Prollenium\SYM 2018-03\Biometrics\Programs\Listing\xxx.sas ran on Month Day Year at hh mm on data from Month Day, Year.

Listing 16.2.7.1.2 – Adverse Events (Excluding Vascular Injections/Visual Events)

Site-Subject	Trt. in PRO	FST	Reported by	System Organ Class// Preferred Term// Verbatim Term	Start Date [Day #]	Stop Date [Day #]	Severity Causality Outcome	Where on face	Action Taken ¹	SAE
xx-xxx	R. Silk	III	Subj/Diary	NERVOUS SYSTEM DISORDERS// HEADACHE // HEADACHE	01JAN2019 2	04JAN2019 5	MILD UNLIKELY STABLIZED	QD1,QD3	1	N

Day # is calculated from baseline (Visit 1) date. Day 1 is the baseline date while Day -1 is the day prior to the baseline visit.

¹ Action Taken: 1=None, 2=Study treatment interrupted/discontinued, 3=Non-drug therapy, 4=New OTC or Rx drug added, 4=Hospitalized

O:\Studies\ Prolenium\SYM 2018-03\Biometrics\Programs\Listing\xxx.sas ran on Month Day Year at hh mm on data from Month Day, Year.

Note:

Repeat Listings 16.2.7.1.1 and 16.2.7.1.2 for AEs that led to study treatment interrupted/Discontinued and Serious AEs –

Listing 16.2.7.2.1 – Adverse Events (Related to Vascular Injections/Visual Events) Leading to Study Treatment Interrupted/Discontinued

Listing 16.2.7.2.2 – Adverse Events (Excluding Vascular Injections/Visual Events) Leading to Study Treatment Interrupted/Discontinued

Listing 16.2.7.3.1 – Serious Adverse Events (Related to Vascular Injections/Visual Events)

Listing 16.2.7.3.2 – Serious Adverse Events (Excluding Vascular Injections/Visual Events)

Listing 16.2.7.4 – Adverse Events (Related to Vascular Injections/Visual Events) Lasted more than 30 Days

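### No planned SAP table pools TEAEs across its two event classes, so the any-TEAE share is absent and a preferred term seen in both classes is split

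*SAP*

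**What the plan says.** Protocol 8.3 sets the plan for adverse events: "Frequency and percentage of subjects reporting TEAEs will be tabulated overall and for each treatment in PRO 2018-02 by preferred terms", then by severity and relationship to the device. A subject counts once per preferred term within an arm, at the strongest grade. The section continues: "In addition, visual related TEAEs will be summarized separately by preferred term".

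SAP 5.6 states: "Key safety variables include incidence rate of treatment-emergent adverse events (TEAEs"; it does not limit this to one type of event.

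SAP 5.6.1 introduces a division of "TEAEs (those related to vascular injections/Visual events, separate from those that were not related to vascular injections/Visual events". It attaches this division to a summary grouped by the number of injections received in the prior study. Its next sentence plans the preferred-term, severity and relationship tabulation for injection-site TEAEs.

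The shells apply the division throughout. Tables 14.3.2.1 to 14.3.2.9 cover the vascular injection/visual class. The last of these is titled "Overall Summary of Treatment-Emergent Adverse Events (TEAEs) Related to Vascular Injections/Visual Events". After it comes the note "Tables 14.3.2.1, 14.3.2.2, 14.3.2.3, 14.3.2.4 will be used as the shell for the following tables", which generates Tables 14.3.3.1 to 14.3.3.4 for everything outside that class. The source listings divide the same way: 16.2.7.1.1 for the first class, and 16.2.7.1.2, "Adverse Events (Excluding Vascular Injections/Visual Events", for the second.

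SAP section 6 presents the shells as examples and adds: "Tables and listings may be modified as needed during the data analyses".

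**The concern.** The protocol treats the visual summary as a supplement to a tabulation of all TEAEs. In the SAP shells, two class-specific sets of tables stand in its place. The study is purely descriptive (SAP 5.1 rules out inferential analysis), so the tables are the result.

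Two things are at stake. First, a reader who wants the proportion of retreated subjects with any TEAE finds two incidences that cannot be added, because one subject can have events in both classes. Second, if a preferred term occurs in both classes, its incidence is spread over two tables, and so are its severity and relationship counts. The single by-term figure that Protocol 8.3 plans then appears nowhere.

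**Working it through.** The plan states no figure on this point, so there is none to reproduce. The check has four steps.

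**1. Count the TEAE tables by class (SAP shells).**
- Vascular injection/visual: 14.3.2.1 to 14.3.2.9, which is 9.
- Excluding these: 14.3.3.1 to 14.3.3.4, which is 4.
- Total 9 + 4 = 13. Tables covering both classes: 0.

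The start of the SAP contents list is missing from the text available. The body of the shells, however, runs from 14.3.1.3 directly to 14.3.2.1 and from 14.3.3.4 directly to 14.3.4.1 (lip function), with no pooled TEAE table at either join.

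**2. Can one subject, or one preferred term, be in both classes?** The first class is wider than rare vascular or ocular events. The any-event row in its shells refers to injection-site or visual TEAEs, and the sample entry in Listing 16.2.7.1.1 is injection site swelling. The sample entry in Listing 16.2.7.1.2 is headache. One subject could have both. Listing 16.2.7.1.1 also carries flags, event by event, for relation to the injection and to vision. If class is assigned from such flags, the same preferred term could fall in either class for different events. The documents do not show that any term will.

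**3. What the tables say about any TEAE.** Let a and b be the numbers of subjects with at least one event in each class, out of N retreated subjects.
- Lower bound: max(a, b), reached when the smaller group lies wholly inside the larger.
- Upper bound: min(N, a + b), reached when overlap is as small as possible.
- Width: min(a, b, N − a, N − b).

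Assumed rates, with N = 100:

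| Class 1 | Class 2 | Any-TEAE range | Width (points) |
|---|---|---|---|
| 2% | 30% | 30% to 32% | 2 |
| 60% | 10% | 60% to 70% | 10 |
| 90% | 10% | 90% to 100% | 10 |
| 30% | 20% | 30% to 50% | 20 |
| 60% | 30% | 60% to 90% | 30 |
| 50% | 50% | 50% to 100% | 50 |

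The last row is the mathematical maximum. N = 157, the largest value below the 158 in the protocol synopsis, gives practically the same ranges.

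**4. A preferred term in both classes.** The same bounds apply within a term. Suppose 5 subjects report it in one class and 3 in the other. Then 5 to 8 subjects have the term: 5/157 = 3.2% to 8/157 = 5.1% at N = 157, or 5/60 = 8.3% to 8/60 = 13.3% at an assumed N of 60. Counts at a given severity or relationship are divided between the same two sets of tables.

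**The case against.** Much of the case on the other side stands.

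- **Protocol 8.3 does not promise an any-TEAE row.** It plans rates by preferred term and a once-per-term counting rule, not a subject's worst grade across terms. A reader might take its word 'overall' to mean all event types together; in context it means across the two prior arms. Measured against the protocol, the shortfall is limited to terms that fall in both classes. The any-TEAE share is missing relative to SAP 5.6, which names TEAE incidence without defining it as an any-event share.
- **The figures are not lost.** A reader might infer that the any-TEAE share can only be bounded. That is true of the tables alone. Both AE listings are by subject, and matching subject numbers gives the exact count.
- **SAP 5.6.1 does not forbid pooling.** Read literally, its dividing sentence governs the number-of-injections summary. The shells extend the division to every table, and section 6 allows them to change. SAP section 1 also says that the plan implements protocol section 8. Permission to change is still not a commitment, and no pooled table or merge of the listings is described.
- **Table 14.3.2.9 is not a protocol departure.** Its duration, outcome and action-taken rows have no second-class table, which a reader might count as a further omission. Protocol 8.3 plans no such summary for any class, so more detail for device-related local events is a legitimate choice.

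**Conclusion.** The point holds as a gap in the planned summaries. All 13 TEAE shells are limited to one class. If the SAP is followed as written, no table gives the share of subjects with any TEAE, and any preferred term with events in both classes has its incidence, severity and relationship counts split, although Protocol 8.3 tabulates TEAEs without that division.

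The size is unknown. Every rate, count and N used above, apart from the upper limit on N, is an assumption. On those assumptions the uncertainty left by the tables runs from 2 to 50 percentage points; it is small if either class is rare or nearly universal. The term-splitting effect also depends on events with one preferred term being allocated to different classes, which the documents allow but do not show. No data are lost and no test is affected. The change is worth making because it is cheap and supplies a headline safety figure.

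**What to change.** Add one sentence to SAP 5.6.1: Tables 14.3.2.1, 14.3.2.2 and 14.3.2.3 will also be run on all TEAEs pooled, by prior arm and in total, with a first row 'Subjects with at least one TEAE'. Apply the existing rule (once per preferred term, at the strongest severity and relationship) to the pooled events, and keep the class tables as subsets.

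A pooled run of Table 14.3.2.9 is optional, for the reason given above.

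The cost is one sentence and three more runs of existing table programs, with no new data. The downside is three extra tables that largely repeat preferred terms from the class tables.
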